### 9.1.2. Secondary endpoint(s)

The secondary endpoints for all patients and the two cohorts of special interest are:

- Overall Survival (OS) from initial TACE is defined as the time interval from the day of the first TACE to death due to any cause. Patients alive at the end of the study will be censored at the last date known to be alive.
- Progression-free survival (PFS) from initial TACE is defined as the time interval measured from the day of the first TACE to documented (radiological or clinical) progression or death, whichever comes first.
- Time to progression (TTP) from initial TACE is defined as the time interval from the day of first TACE to the date of documented progression. Patients without tumor progression at the end of the study will be censored at their last date of tumor evaluation.
- Tumor response to TACE by mRECIST will be evaluated according to the categories “Complete Response”, “Partial Response”, “Stable Disease”, and “Not evaluable” by mRECIST for each TACE.
- Duration of TACE treatment is defined as the time interval from of the day of first TACE to the date of permanent discontinuation of TACE (when an investigator decides TACE is no longer applicable regardless of the reason for discontinuation including death).
- TACE unsuitability will be determined according to the selected guidelines including AASLD, APASL, JSH, EASL-EORTC guidelines ...etc.
- Time to TACE non-eligibility will be determined according to the selected guidelines including AASLD, APASL, JSH, EASL-EORTC guidelines ...etc.
- Deteriorations of liver dysfunction will be evaluated throughout the study. Deteriorations of liver dysfunction are defined as below
  - Deterioration of Child-Pugh score (A5, A6, B7, B8, B9)
  - Liver dysfunction reported as AE or deterioration of AST, ALT or Bilirubin (from Grade1 to Grade 2-5, from Grade 2 to 3-5, Grade 3 to Grade 4 or 5.)
  - Any liver related adverse events or deterioration of liver related events according to CTCAE Version 4.03
  - Change of liver related lab data (AST, ALT, Bilirubin, Alb, INR)

Specific secondary endpoints for patients treated with sorafenib are:

- Overall survival (OS) from initiation of sorafenib is defined as the time interval measured from start date of sorafenib treatment to death due to any cause. Patients alive at the end of study will be censored at the last date known to be alive.

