- Progression-free survival (PFS) from initiation of sorafenib is defined as the time interval measured from the start date of sorafenib treatment to documented (radiological or clinical) progression or death, whichever comes first.
- Time to progression (TTP) from initiation of sorafenib is defined as the time interval from start date of sorafenib treatment to the date of documented progression. Patients without tumor progression at the end of the study will be censored at their last date of tumor evaluation.
- Duration of sorafenib treatment is defined as the time interval from start date of sorafenib treatment to the date of permanent discontinuation of sorafenib treatment (regardless of the reason for discontinuation including death).
- The tumor status at different visits response according to mRECIST will be evaluated according to the categories “Complete Response”, “Partial Response”, “Stable Disease”, “Clinical Progression”, “Radiological Progression”, and “Not evaluable at this visit”. The best overall response will be analyzed providing absolute and relative frequencies of the tumor status categories.
- Incidence of Treatment-emergent Adverse Events (TEAEs) – patients will be monitored for TEAEs using the NCI-CTCAE Version 4.03. Details on the collection, management and reporting of TEAEs can be found in section 11.

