### **9.7.8. Bias, confounding and effect-modifying factors**

As the study aims to compare two non-randomized cohorts of patients as defined in 9.7.4, all factors probably influencing treatment assignment as well as the outcome have to be taken into account to avoid false positive or false negative interpretation of data. It will be tried to control for the effect of confounders using propensity score based methods (see 9.7.4). Possible confounders are:

- Demography (age, gender)
- Etiology (Hepatitis C, Hepatitis B, alcoholic)
- Previous treatment (hepatectomy, number of previous TACE)
- Response to the last TACE
- Barcelona-Clinic Liver Cancer (BCLC) Stage at the time of TACE non-eligibility
- Liver dysfunction: Child-Pugh status at the time of TACE non-eligibility
- Tumor size at the time of TACE non-eligibility
- Vascular invasion at the time of TACE non-eligibility
- Extrahepatic spread at the time of TACE non-eligibility
- Number of lesions at study entry: at the time of TACE non-eligibility
- Physicians' speciality
- Region

A complete list of expected confounders will be added to the SAP.

It is important to note that the propensity score method can only account for confounders that have been measured in the study, but of course not for any unknown or unmeasured confounders. As a consequence, it cannot be ensured that the resulting hazard ratio estimation is completely free of bias and thus the results have to be interpreted with care.

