#### Target lesion assessment

The investigator will measure each target lesion in the same manner as at baseline. Extrahepatic non-nodal lesions will be measured using their longest diameter. Malignant lymph nodes (excluding those in the porta hepatis, which can never be target lesions) will be measured in short axis diameter. Intrahepatic target lesions will be measured in the longest diameter that shows typical HCC enhancement (excluding areas of necrosis).

If a lesion decreases in size to the point where it is still present, but cannot be measured accurately, a default value of 5 mm should be recorded for its diameter. If a lesion has disappeared, a value of 0 mm should be recorded for its diameter. If a lesion has split into distinct fragments, the longest diameter of each fragment should be measured, and the diameters added together. If two lesions have merged, the longest diameter of the entire resulting lesion should be measured.

The sum of diameters will be calculated by adding all target lesion diameters. The sum of diameters is always compared to two reference points: the baseline sum of diameters, and the smallest sum of diameters seen during the trial (also called the nadir). The baseline may actually be the nadir, if there has been no reduction in the sum of diameters during the trial. The target lesion response is then classified as follows:

Target lesion response	
Complete response (CR)	Complete disappearance of target lesions outside the liver Complete disappearance of typical HCC enhancement from all target liver lesions All target lymph nodes <10 mm
Partial response (PR)	At least a 30% decrease in the sum of diameters from baseline
Progressive disease (PD)	At least a 20% increase in the sum of diameters from the smallest value seen during the trial (including baseline), with at least a 5 mm absolute increase in the sum
Stable disease (SD)	Neither enough shrinkage to qualify as PR, nor enough growth to qualify as PD
Non-evaluable (NE)	One or more target lesions not evaluated because of imaging issues, coverage, or change in imaging technique
Please note that when lymph nodes are included as target lesions, a CR may occur even when the sum of diameters is not zero, since a normal lymph node will have a diameter greater than zero but less than 10 mm.	

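### The categories for tumor response to each TACE omit progressive disease, contradicting the protocol's own mRECIST annex and its sorafenib response endpoint

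*Protocol*

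**What the plan says.** Protocol section 9.1.2 defines tumor response to TACE as "evaluated according to the categories “Complete Response”, “Partial Response”, “Stable Disease”, and “Not evaluable” by mRECIST for each TACE". The list reads as closed, with four levels and none for progression.

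For patients on sorafenib, the same section lists tumor status by mRECIST with complete response, partial response and stable disease, and then "Clinical Progression”, “Radiological Progression”, and “Not evaluable at this visit".

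The mRECIST text in section 16.5 (Target lesion assessment) defines three levels that matter here:

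- PD: "At least a 20% increase in the sum of diameters from the smallest value seen during the trial", with an absolute increase of at least 5 mm.
- SD: "Neither enough shrinkage to qualify as PR, nor enough growth to qualify as PD".
- NE: "One or more target lesions not evaluated because of imaging issues, coverage, or change in imaging technique".

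The non-target lesion table and both visit-response tables in section 16.5 also contain PD.

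The per-TACE result is used in two places: the secondary objective on response by number of TACEs (section 8.2), and the summary of response to each TACE by procedure and region (section 9.7.7). Section 9.7.8 also names "Response to the last TACE" among the possible confounders. It gives no levels and leaves the complete confounder list to the SAP.

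**The concern.** A response endpoint said to follow mRECIST should carry every mRECIST outcome. The one left out is the unfavourable one.

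The protocol expects such patients. Section 9.3.8 includes, among the non-eligibility criteria, repeated new liver lesions on CT after TACE and TACE failure as judged by the investigator. Under section 16.5, a new liver lesion of at least 1 cm with typical enhancement is progression, whatever the other lesions show.

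If tables are built from the four levels as listed, the response distribution at each TACE is wrong for a stated secondary objective, and a reader of the report could not see how often TACE was followed by progression. If the covariate in section 9.7.8 were built from the same list, progressors could be pooled with stable or unevaluable patients in the propensity score.

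**Working it through.** The protocol attaches no figure to this endpoint, so there is none to reproduce. Its one power figure (83%) concerns overall survival and does not depend on the response categories.

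**Step 1. Compare the category lists.**

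| Place in protocol | Levels | Progression levels |
|---|---|---|
| 9.1.2, response to each TACE | CR, PR, SD, NE | 0 |
| 9.1.2, tumor status on sorafenib | CR, PR, SD, clinical progression, radiological progression, NE | 2 |
| 16.5, target lesions | CR, PR, PD, SD, NE | 1 |
| 16.5, visit response with target and non-target lesions | CR, PR, SD, NE, PD | 1 |

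Four of the five visit-response levels appear in the TACE list. PD is the one missing.

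**Step 2. Can another level absorb a progressor?** Not under the annex definitions. SD requires too little growth for PD, and NE requires that lesions were not evaluated. CR and PR are excluded because PD in target lesions, PD in non-target lesions or a new lesion makes the visit response PD.

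**Step 3. Do other endpoints supply the information?** PFS and TTP in section 9.1.2 run from the first TACE to documented progression, one time per patient. Response is assessed against the most recent TACE and recorded for each TACE (section 9.3.9). One progression time from the first TACE does not give the response distribution at the second or a later TACE.

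**Step 4. Size under each possible handling.** Let r be the true CR+PR share of all assessed TACEs and q the share that are PD. The protocol gives neither. Assume r = 40% or 30% and q = 10%, 20% or 30%.

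- *Progressors coded SD.* CR+PR stays at r and the SD share rises by q. If no assessment is truly unevaluable, CR+PR+SD is 1 − q = 90%, 80% or 70%, but reads 100%.
- *Progressors coded NE and kept in the denominator.* CR+PR stays at r. The NE share rises by 10, 20 or 30 percentage points, so progression looks like missing data.
- *Progressors leave the denominator.* Apparent rate = r / (1 − q):

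| True rate r | q = 10% | q = 20% | q = 30% |
|---|---|---|---|
| 40% | 0.40/0.90 = 44.4% | 0.40/0.80 = 50.0% | 0.40/0.70 = 57.1% |
| 30% | 0.30/0.90 = 33.3% | 0.30/0.80 = 37.5% | 0.30/0.70 = 42.9% |

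In the third case, the comparison by number of TACEs is distorted whenever q differs between TACEs. For instance, a constant true rate of 40% would read 44% where q = 10% and 57% where q = 30%. The protocol has no figure for how q changes with the number of TACEs.

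**The case against.** The best defence is that this is a slip in one sentence which the rest of the protocol corrects. The sentence invokes mRECIST, and the annex supplies PD. Coding a progressor as SD or NE would break the annex. Section 9.3.9 and Table 2 collect response to the most recent TACE without restricting the categories, and section 9.3.9 also allows other criteria. The CRF is not shown and may well carry PD. Progression still reaches PFS and TTP, and TACE failure has its own items in section 9.3.8.

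Much of this stands, and it rules out several stronger readings that a reader might infer:

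- *Progressors will be misclassified or dropped.* No text says how they are coded, and section 9.1.2 defines neither a response rate nor an evaluable denominator. The inflated rates describe one of three possible handlings.
- *The propensity covariate loses its key level.* Section 9.7.8 neither defines levels for "Response to the last TACE" nor links it to the list in section 9.1.2.
- *The upward bias grows at later TACEs.* No figure in the protocol supports this.
- *PD is the event that triggers non-eligibility.* None of the criteria in section 9.3.8 is worded as mRECIST PD. They overlap with it only in part, and several can already be met at enrollment.

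The defence does not remove the contradiction. The protocol fixes the list explicitly, so this is not a detail left to the SAP: an SAP that follows the list inherits the gap, and one that adds PD departs from the protocol. PFS and TTP do not replace a per-TACE result.

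**Conclusion.** The omission is certain and wrong as written: section 9.1.2 conflicts with section 16.5 and with the sorafenib endpoint beside it. If the list is applied literally, response by number of TACEs and response to each TACE by procedure would be distorted.

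The form and size depend on handling that the protocol does not state. The CR+PR rate is unchanged if progressors are coded SD or are kept in the denominator as NE, although progression is then hidden. It rises by a factor of 1/(1 − q) if they leave the denominator. The PD shares and true rates used here are assumptions.

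The definition of overall survival, the sample size and the power are unaffected. An effect on the primary hazard ratio could arise only if the covariate in section 9.7.8 is built from the defective list. The protocol does not establish that, so it remains a conditional risk. The point is a correction worth making to a secondary endpoint.

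**What to change.** In section 9.1.2, list the response to each TACE as: Complete Response, Partial Response, Stable Disease, Progressive Disease (radiological or clinical), Not evaluable. State that all assessed TACEs are in the denominator. Confirm that the CRF item for response to the most recent TACE carries progression.

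If "Response to the last TACE" is built from this list, give it the same full set of levels plus one for patients with no TACE before non-eligibility. That extra level is needed because section 9.1.1 places pre-existing non-eligibility at enrollment, and section 9.2.2 allows an earlier TACE without requiring one.

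The cost is one list entry and a table shell, provided the CRF already captures progression for this item. If it does not, PD per TACE would have to be derived from the recorded tumor assessments and progression dates, which is more work. Last patient last visit is planned for Q2 2017 and this version dates from September 2015, so the change can precede the final analysis.

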This study is an international, prospective, open-label, multi-center, non-interventional study to evaluate outcomes of all patients who are treated with TACE followed by sorafenib and patients who did not receive sorafenib after TACE. In contrast to the GIDEON study, where pre-treatment with TACE was documented retrospectively, this study will collect more detailed information concerning TACE treatments in a prospective manner. This will enable us to evaluate the time to meet non-eligibility criteria according to this protocol (see 9.1.1.).

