### **8.2. Secondary objective(s)**

Secondary objectives are:

- To evaluate progression-free survival (PFS), time to progression (TTP), tumor response and AE from time of TACE non-eligibility overall and in the cohorts of special interest
- To evaluate overall survival (OS), progression-free survival (PFS), time to progression (TTP), tumor response and AE from start of sorafenib treatment.
- To determine duration of treatment (DOT) of sorafenib after TACE with respect to the start of sorafenib treatment (early vs. not early).
- To determine time to meet TACE non-eligibility criteria from initial TACE according to the guidelines
- To determine the proportions of patients who receive sorafenib after TACE and those who do not receive sorafenib after TACE, respectively, regionally and globally
- To evaluate response to TACE by number of TACEs
- To evaluate deterioration of liver dysfunction in the course of TACE treatment and thereafter.
- To evaluate OS from initial TACE for all patients in the study irrespective of their treatment after TACE
- To evaluate deviations from recommendations for TACE use in the treatment guidelines for TACE use, regionally and globally
- In addition, practice patterns of the physicians involved in the care of patients with HCC under real-life conditions will be evaluated.

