### 9.1.1. Primary endpoint(s)

The primary endpoint is overall survival (OS) from time of TACE non-eligibility.

OS is defined as the time interval from TACE non-eligibility to death due to any cause. Patients alive at the end of study will be censored at the last date known to be alive.

A patient is classified non-eligible for TACE, if at least one of the criteria in 9.3.8 except ‘advanced liver disease (Child-Pugh class B or C) is met.

Time of TACE non-eligibility is the first point in time in the study when TACE non-eligibility is met according to the documentation in the CRF. In case of a pre-existing TACE non-eligibility, time of TACE non-eligibility will be defined as the time of enrollment.

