## **9.2. Setting**

### **9.2.1. Eligibility**

Patients enrolled in this study have a diagnosis of unresectable HCC in whom a decision to treat with TACE has been made at time of study enrollment.

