### **9.2.2. Inclusion criteria**

- Patients with histologically/cytologically documented or radiographically diagnosed HCC. Radiographic diagnosis needs typical findings of HCC by radiographic method i.e. on multi-dimensional dynamic CT, CT hepatic arteriography (CTHA)/CT arterial portography (CTAP) or MRI.
- Patients with BCLC stage B or higher.
- Patients in whom a decision to treat with TACE has been made at time of study enrollment. Patients that have received one TACE in the past also can be enrolled, if the TACE was done at the same site and all required data about such previous TACEs are available. TACE

includes both conventional TACE with lipiodiol (or similar agents) and chemotherapeutic agent(s) and TACE with DC Beads® excluding TAE without chemotherapeutic agent.

- Patients with unresectable HCC (incurable with curative treatments including resection or ablation or not eligible for resection or local ablation)
- Patients must have signed an informed consent form
- Patients must have a life expectancy of at least 8 weeks

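### Time to TACE non-eligibility has two criteria sets and no restriction to patients at risk, so under the 9.1.1 date patients already non-eligible at entry contribute zero or artificial times

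*Protocol*

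**What the plan says.** **Guideline-based text.** The secondary objective in Protocol 8.2, repeated in the study information table and the abstract, is "To determine time to meet TACE non-eligibility criteria from initial TACE according to the guidelines". The matching endpoint in 9.1.2, introduced as applying to all patients and to the two cohorts of special interest, reads "Time to TACE non-eligibility will be determined according to the selected guidelines including AASLD, APASL, JSH, EASL-EORTC guidelines ...etc". The bullet just above it, TACE unsuitability, refers to the same open list of guidelines.

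**Protocol-based text.** The rationale in section 7 says of the prospective TACE data: "This will enable us to evaluate the time to meet non-eligibility criteria according to this protocol (see 9.1.1", a reference to the primary endpoint section. There the rule is "A patient is classified non-eligible for TACE, if at least one of the criteria in 9.3.8 except" Child-Pugh class B or C is met, and the date is the first time in the study that this is documented. For patients who are non-eligible from the outset, 9.1.1 adds: "In case of a pre-existing TACE non-eligibility, time of TACE non-eligibility will be defined as the time of enrollment".

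**Entry.** Section 9.2.2 has two routes. The main one is "Patients in whom a decision to treat with TACE has been made at time of study enrollment". The second is "Patients that have received one TACE in the past also can be enrolled, if the TACE was done at the same site". BCLC stages B and above may enter. The list in 9.3.8 is checked at the initial visit and includes ECOG PS of 1 or more, BCLC C or D, vascular invasion and extrahepatic spread.

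**The concern.** Two things go wrong together.

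First, the criteria. A patient's non-eligibility date under the 9.3.8 list need not equal the date under any one guideline, and the guideline list is not closed. The date that starts the primary survival clock and the date reported under the same name as a secondary endpoint can then differ for the same patient.

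Second, the risk set. A time-to-event estimate should start with patients who have not yet had the event. The endpoint is stated for all patients, and entry is open to patients who already meet a criterion. Under the 9.1.1 date their recorded time reflects when they were enrolled, not when they stopped being eligible.

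At stake is the interpretation of a result that the protocol presents as something its prospective data collection makes possible, where the preceding observational study recorded TACE only in retrospect.

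**Working it through.** **The plan's own figure.** The protocol gives no number for this endpoint. Its only power figure is for overall survival (9.5): 250 per cohort, medians of 9 and 12 months, 18 months of enrolment, 36 months in total, one-sided 2.5%. Exponential survival with uniform accrual gives death probabilities of 0.865 and 0.780, so 250 × (0.865 + 0.780) ≈ 411 deaths. With hazard ratio 9/12 = 0.75, the Schoenfeld formula gives z = √(411.2 × 0.25) × |ln 0.75| − 1.96 ≈ 0.96, a power of 83.1%. The stated 83% reproduces, and nothing below touches it.

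**Step 1: what the interval becomes.** Interval = date of non-eligibility − date of first TACE (origin from 8.2). For a patient non-eligible from the outset, the 9.1.1 date is enrolment. The day counts below are examples; the protocol gives no such gaps.

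| Entry route | Enrolment relative to first TACE | Interval |
|---|---|---|
| Decision to treat made, TACE still to come | 14 days before | −14 days |
| Same route | same day | 0 days |
| One earlier TACE | 60 days after | +60 days |

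The first two are zero or below. The third is positive but is only the lag between the earlier TACE and enrolment.

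**Step 2: effect on the overall median (illustration).** Let a share f of patients sit at time zero or below, and let the rest be exponential with median m. Both f and m are assumptions. The overall median solves

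(1 − f) × exp(−λt) = 0.5, with λ = ln 2 / m,

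so t = (m / ln 2) × ln[(1 − f) / 0.5], and t is zero or below once f reaches 50%.

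For m = 6 and f = 0.2: (6 / 0.693) × ln 1.6 = 4.07. For f = 0.4: (6 / 0.693) × ln 1.2 = 1.58.

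| f | m = 6 months | m = 12 months |
|---|---|---|
| 10% | 5.1 | 10.2 |
| 20% | 4.1 | 8.1 |
| 30% | 2.9 | 5.8 |
| 40% | 1.6 | 3.2 |
| 50% or more | ≤ 0 | ≤ 0 |

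Restricting the estimate to patients at risk returns m in every row. The table covers only the share at zero or below. Patients with one earlier TACE are outside it, because they contribute a lag instead.

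**Step 3: which criteria set governs.** The objective (8.2) and the endpoint (9.1.2) point to guidelines. The rationale (section 7) points to 9.1.1. Following either one departs from the other. Under the guideline reading the protocol gives no date at all for a patient who already meets a guideline criterion at the first TACE, so the question of who is at risk remains.

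**The case against.** The texts that actually set this endpoint agree with each other: objective and endpoint both say guidelines. Only one sentence in the background ties the interval to 9.1.1. The enrolment-date rule was written to start the primary survival clock, and 9.1.2 does not invoke it. A protocol may date its primary index one way and report guideline timing separately. Section 9.7.1 also leaves calculated variables to the SAP, which is not among the documents at hand. The analysis is descriptive.

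Much of this stands. The 9.1.1 date reaches this endpoint only through the shared term and the section 7 cross-reference, so the zero times are conditional on that reading. Naming the selected guidelines could be left to an SAP. What remains is that the protocol answers the question of criteria in two ways and assigns the endpoint to all patients. An SAP that leaves out patients already non-eligible would depart from that wording.

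A reader might also infer that every patient non-eligible at entry gets a zero or negative time. That does not follow. Patients enrolled after one TACE get a positive one, and a negative value needs enrolment before the day of the first TACE. Section 9.2.1 requires only that "a decision to treat with TACE has been made at time of study enrollment" and gives no gap.

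**Conclusion.** The point holds in a limited form. The same named time is tied to guidelines in 8.2 and 9.1.2 and to the protocol criteria in section 7. If the 9.1.1 date is used for all patients, those already non-eligible at entry add either times of zero or below, which pull the estimate down, or administrative lags. Neither measures becoming non-eligible.

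The size cannot be fixed from the protocol. It rests on the share non-eligible at entry, which is not given, and on an assumed exponential time in the rest. The entry criteria and 9.3.8 show that such patients can be enrolled, not how many there will be.

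One might go further and call the result unusable. The documents do not support that. The interval stays well defined for patients meeting no criterion at first TACE, and because 9.3.8 is completed at the initial visit, patients already meeting a protocol criterion can be identified. Nor do they support a claim against the primary analysis: overall survival and its 83% power are unaffected.

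**What to change.** 1. In 9.1.2, restrict the endpoint to patients who meet none of the applicable criteria at first TACE, counted from that TACE. Report patients already non-eligible as a proportion.
2. Reconcile sections 7, 8.2 and 9.1.2. Either name one criteria set for this endpoint, or keep both and give the 9.1.1-based and guideline-based times distinct names. Which to choose is the sponsor's decision.
3. Wherever guidelines are used, replace the open-ended list with a closed list of named guidelines.

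The cost is wording in three sections and one restriction of the analysis set. No new data are needed for the 9.1.1-based time, since the 9.3.8 criteria are already recorded at the initial visit. The drawback is fewer patients in this descriptive endpoint.

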## **11. Management and reporting of adverse events/adverse reactions**

### **11.1. Definition**

An adverse event (AE) is any untoward medical occurrence in a patient administered a medicinal product and which does not necessarily have to have a causal relationship with this treatment. An AE can therefore be any unfavorable and unintended sign (e.g. an abnormal laboratory finding), symptom, or disease temporally associated with the use of a medicinal product, whether or not considered related to this medicinal product.

The term also covers laboratory findings or results of other diagnostic procedures that are considered to be clinically relevant (e.g. that require unscheduled diagnostic procedures or treatments or result in withdrawal from the study).

The AE may be:

- A new illness
- Worsening of a sign or symptom of the condition under treatment or of a concomitant illness
- An effect of the study medication
- An effect of the comparator drug
- An effect related to study procedure
- Any combination of one or more of these factors
- An effect related to lack of drug effect,
- Medication error, overdose, drug abuse, drug misuse or drug dependency itself, as well as any resulting event
- Drug exposure via mother/ father (exposure during conception, pregnancy, childbirth and breastfeeding)

- An effect related to pre-existing condition improved (unexpected therapeutic benefits are observed)

As mentioned above no causal relationship with a study medication is implied by the use of the term “adverse event”.

An Adverse Drug Reaction (ADR) is any AE suspected as having a reasonable causal relationship to the studied drug. It is defined as a response to a drug, which is noxious and unintended and which occurs at doses normally used in man for prophylaxis, diagnosis, or therapy of disease or for modification of physiological function.

An AE is serious if it:

- Results in death
- Is life-threatening
- Requires inpatient hospitalization or prolongation of existing hospitalization (see exceptions below)
- Results in persistent or significant disability or incapacity
- Is a congenital anomaly or birth defect
- Is medically important.

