## 16.4. Liver Status – Child-Pugh Classification

### Points Scored for Observed Findings

	Points Scored for Observed Findings		
	1	2	3
Encephalopathy grade a	None	1 or 2	3 or 4
Ascites	Absent	Slight	Moderate
Serum bilirubin, mg/dL	< 2	2 to 3	> 3.0
Serum albumin, g/dL	> 3.5	2.8-3.5	< 2.8
Prothrombin time, sec (prolonged)	< 4	4-6	> 6

a \*Encephalopathy grades:

Grade 0: normal consciousness, personality, neurological examination, electroencephalogram

Grade 1: restless, sleep disturbed, irritable/agitated, tremor, impaired handwriting, 5 cps waves

Grade 2: lethargic, time-disoriented, inappropriate, asterixis, ataxia, slow triphasic waves

Grade 3: somnolent, stuporous, place-disoriented, hyperactive reflexes, rigidity, slower waves

Grade 4: unrousable coma, no personality/behavior, decerebrate, slow 2-3 cps delta activity

Assessment as good operative risk (A) if 5 or 6 points; moderate risk (B) if 7 to 9 points, and poor operative risk (C) if 10 to 15 points (developed for surgical evaluation of alcoholic cirrhotics).

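### The laboratory grade-shift rule for liver deterioration has no line for a normal starting value, and the Child-Pugh list leaves class C unclear

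*Protocol*

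**What the plan says.** Section 8.2 of the protocol makes this a secondary objective: "To evaluate deterioration of liver dysfunction in the course of TACE treatment and thereafter". Section 9.1.2 then defines the endpoint, for all patients and for the two cohorts of special interest, by four bullets:

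1. "Deterioration of Child-Pugh score (A5, A6, B7, B8, B9", with the list closed after B9.
2. An alternative, "Liver dysfunction reported as AE or deterioration of AST, ALT or Bilirubin", where the laboratory part is spelled out as "deterioration of AST, ALT or Bilirubin (from Grade1 to Grade 2-5, from Grade 2 to 3-5, Grade 3 to Grade 4 or 5".
3. "Any liver related adverse events or deterioration of liver related events according to CTCAE Version 4.03".
4. "Change of liver related lab data (AST, ALT, Bilirubin, Alb, INR".

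The section does not say how the four bullets combine, or whether a shift is measured from baseline or from the preceding visit. It also does not say whether the Child-Pugh list gives starting scores or all the scores considered. Section 9.7.7 adds a summary of the same endpoint by TACE procedure and region. Annex 4, section 16.4, gives the full Child-Pugh scale, with "poor operative risk (C) if 10 to 15 points", and section 9.3.8 records class B or C as a criterion at the initial and every follow-up visit.

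**The concern.** A rule for deterioration should not score a larger worsening as nothing and a smaller one as an event. As written, bilirubin going from normal to Grade 3 meets no line of the shift rule, while Grade 1 to Grade 2 does. The patients affected are those who start with the best values on a parameter.

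The groups compared or tabulated (early versus not early sorafenib, TACE procedures, regions) are not randomised. If they differ in the share of patients with a normal starting value, the shift limb will differ between them for that reason alone. A reader could take this for a difference in hepatic tolerability.

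The Child-Pugh bullet raises a lesser question. Class C is on the protocol's scale and is recorded at visits, but no C score is listed.

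**Working it through.** The protocol states no figure for this endpoint, so there is nothing to reproduce. The check is an enumeration.

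**Laboratory grades.** Inputs: the shifts listed in section 9.1.2, and a scale of 0 to 5 with 0 meaning normal (my assumption; the protocol names only Grades 1 to 5 here).

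- Worsening steps possible: 5 + 4 + 3 + 2 + 1 = 15.
- Listed: from Grade 1, 4 steps; from Grade 2, 3 steps; from Grade 3, 2 steps. Total 9.
- Omitted: 15 − 9 = 6, namely 0 to 1, 0 to 2, 0 to 3, 0 to 4, 0 to 5, and 4 to 5.

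The four steps from 0 to Grade 2 or higher matter most. Grade 4 to 5 is minor. Omitting 0 to 1 can be defended as a choice of threshold.

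**Reference time point.** If shifts are measured from baseline, a patient who starts at Grade 0 on a parameter can never have an event on that parameter in this limb. If they are measured from visit to visit, a path 0 to 1 to 2 is counted at the second step, and only direct jumps (and 0 to 1) are missed. Section 9.2.5 assumes 6 to 12 weeks between status assessments, so a direct jump between two recorded values is possible.

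**Effect on the limb's rate.** Let g be the share of patients at Grade 0 on a parameter and r the true shift risk. Suppose r is the same at every starting grade and shifts are measured from baseline. The limb then records (1 − g) × r instead of r. Two groups with the same r but shares g1 and g2 would show a ratio of (1 − g1)/(1 − g2), which differs from 1 whenever g1 and g2 differ. The protocol gives neither g nor r.

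**Child-Pugh.** Inputs: the list A5 to B9 and the annex scale of 5 to 15.

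- Worsening steps possible: 10 + 9 + … + 1 = 55.
- Within A5 to B9: 10. From A5–B9 into C10–C15: 5 × 6 = 30. Within C: 15. Sum 55.
- If the list means starting scores, it covers 10 + 30 = 40 and omits only the 15 steps within class C.
- If the list means all scores considered, it covers 10 and omits 45.

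A5 is the lowest score on the scale, so no patient can worsen to A5. The list therefore cannot be one of outcomes alone, and starting scores is the more natural reading.

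**The case against.** The strongest reply is that the shift list is only half of one bullet among four. The adverse-event parts carry no restriction on the starting grade, and section 11.1 says of adverse events: "The term also covers laboratory findings or results of other diagnostic procedures that are considered to be clinically relevant". Section 11.2 requires adverse events to be documented from the first TACE onwards. A rise from normal to Grade 3 thus has a route into the endpoint. One could even see a design in this, with new dysfunction entering as an adverse event and existing dysfunction through the shift list. Adverse events are also summarised by CTCAE grade under section 9.7.6 whatever the starting value, and section 9.7.1 leaves calculated variables to the statistical analysis plan.

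Much of this stands. A reader might infer that patients with normal starting values, or those reaching Child-Pugh C, drop out of the endpoint altogether. The protocol does not support that. The adverse-event bullets can catch them, and on the starting-score reading every move from A5–B9 into class C is counted. Even on the narrower reading, a patient going A6 to B8 to C10 is counted at the first step if steps are judged visit to visit.

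Two things do not stand. First, the other bullets do not replace the missing line. The adverse-event route depends on the investigator judging a laboratory value clinically relevant, in routine practice across about 30 countries. The laboratory-change bullet has neither direction nor threshold, so it is either purely descriptive or would count improvement too. The shift limb is the only laboratory limb with an objective threshold. Second, this is not a detail left open for the analysis plan. The protocol writes an explicit rule, and a plan that added Grade 0 would depart from it.

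**Conclusion.** The concern holds for the laboratory shift limb. As written, it does not count a direct rise from normal to Grade 2 or higher in AST, ALT or bilirubin, although it counts the smaller rise from Grade 1 to 2. The limb under-counts deterioration, and its rate depends on the share of normal starting values in each group. The Child-Pugh part is an ambiguity only: on the natural reading, just the steps within class C are omitted.

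The size of the under-count cannot be derived from the protocol. A reader might put the Grade 0 share at, say, 40–70% and conclude that the deterioration rate is understated by as much. That would need an assumed share, equal shift risk at every starting grade, and shifts measured only from baseline, none of which the protocol states. Even then it would describe this limb and not the four-bullet endpoint.

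The enumeration assumes only that normal is Grade 0. The primary endpoint, overall survival from TACE non-eligibility, is unaffected.

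**What to change.** In section 9.1.2:

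- Define the laboratory shift as any increase to Grade 2 or higher from Grade 0 or 1, or any increase of at least one grade from Grade 2 or higher. This covers 14 of the 15 worsening steps (the 9 listed, the four from 0 to Grade 2 or higher, and 4 to 5). It leaves out only 0 to 1, by choice of threshold.
- Name the reference time point for the shift.
- State that any increase in Child-Pugh score counts, including into and within class C.

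The cost is an edit to the definition and a programming rule. The laboratory values (section 9.3.4) and Child-Pugh scores (section 9.3, Table 2) are already collected, so no new data are needed. The counted deterioration rate may rise.
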